## Section G: Sample Size/Data Analysis

### G1. Sample Size

How many subjects (or specimens, or charts) will be used in this study?

Local: 300            Worldwide: 300

Please indicate why you chose the sample size proposed:

Effectiveness Aims. In our most recent primary care trial, we found moderate effect sizes for both primary ( $g = .40 - .50$ ) and secondary ( $g = .40 - .57$ ) measures. These effects are within the range of effect sizes reported for other trials of CBT and pharmacotherapy for late-life anxiety. Estimated sample sizes will be adjusted for study attrition, defined by failure to complete 6- and 9-month assessments. This team's prior studies have suggested study attrition ranging from 19% to 25%. Study attrition in our pilot community work is even lower (12%; H-30928.), potentially due to flexibility with regard to delivery options that minimize access barriers. Thus, we expect roughly 15% study attrition, but data analytic methods will employ multiple imputation procedures to use data from all participants. Study attrition will be minimized with provision of clear information about the project at the time of outreach and recruitment, the use of telephone-based assessments and person-centered treatment materials and procedures, and reminder calls. Reasons for withdrawal will be recorded. If differential study attrition occurs across groups, measures different by attrition status will be included as covariates in effectiveness outcome analyses. A 2-tailed type 1 error rate of 0.05 was used to calculate sample size. With 64 participants per group (total = 128), we will have 80% power to detect moderate group differences ( $d = .50$ ) in primary and secondary outcomes. Given potential attrition of 15%, we will randomize 150 subjects (75/group). Exclusion rates in prior studies have been 50% or greater

(H-23798, H-30928), which means we will need to enroll at least 300 participants in order to include and randomize 150. Implementation Aims. A purposive sampling strategy will be used for the qualitative interviews targeting CL participants defined as high and low performers. In qualitative research, sampling is completed when categories are saturated (ie, when the targeted group no longer provides new information). No more than 15 interviews are expected from each CL subset (high- and low-performing participants; maximum 30 participant interviews).

Exploratory Aims. Assuming a medium effect size for models that include treatment group and an individual moderator, exploratory aims addressing interactions between treatment group and a moderator predicting 6-month outcomes will have 80% power to capture a change in R-square as small as .03.

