Specific Aim 1. Examine the comparative effectiveness of CL and ECC in older adults with clinically significant worry on primary outcomes (worry, GAD-related symptoms). Primary outcome analyses at 6 months will be intention-to-treat (ITT) and will use the multiple imputation procedures PROC MI and MINANALYZE in SAS Version 9.3 to estimate missing observations. Another set of analyses will be for completers and will include only observed data. We will first employ Analysis of Covariance (ANCOVA) to examine treatment differences in worry and anxiety at 6 months (post intervention). We will conduct separate models for worry and anxiety. All models will include treatment group (ie, CL versus ECC) as a predictor and respective baseline scores and any demographic or clinical variables that differed between treatment groups at baseline as covariates. Treatment effect sizes will be calculated. We will calculate intraclass correlation coefficients (ICC) for both primary outcomes to determine the degree of clustering within referral source (social service or faith-based setting). If a substantial proportion of variability in either outcome is accounted for by referral source (ie, ICC greater than 0.10), multilevel models will be employed using SAS PROC MIXED to minimize the bias of error terms that may occur from dependency due to nesting effects. These models will include the intercept as a random effect and treatment group, respective baseline scores, and variables that differed between treatment groups at baseline as fixed effects.

Specific Aim 2. Examine the comparative effectiveness of CL and ECC on secondary outcomes (anxiety, depression, sleep, functional status, quality of life, service use). Analyses will be conducted as in Aim 1, first using ITT and multiple imputation to estimate missing data. Another set of analyses will be conducted for study completers. We will use ANCOVA to examine treatment differences at 6 months in secondary outcomes (anxiety, depression, sleep, functional status, quality of life, service use), using separate models for each measure. Effect sizes will be calculated. As in Aim 1, these models will include the intercept as a random effect and treatment group, baseline scores, and variables that differed between treatment groups at baseline

as fixed effects.

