**Heterogeneity of Treatment Effects (HTE).** According to PCORI Methodology Standards, exploratory analyses will examine HTE to address for whom and under what conditions CL may be optimally useful. Although sample size may not be adequate to confirm sources of HTE, these exploratory analyses will allow us to describe patterns that can be examined in subsequent larger studies. HTE variables of interest include potential moderators and mediators of treatment effects. Potential moderators include demographics, baseline symptoms (PSWQ, PHQ-8), presence-absence of DSM diagnoses (anxiety disorders, depression), and baseline medication use. Moderation will be tested by including each separate moderator and the interaction term between treatment condition and the moderator in the ANCOVA models described previously. A significant interaction between treatment group and moderator will indicate that differences in treatment effects depend on the moderator. Simple slopes analyses will be conducted to follow-up significant interactions. Potential mediators include change in self-reported use of medication. Medications will be characterized as in our prior trials as antianxiety (benzodiazepine, buspirone, or other), antidepressant (SSRI, SNRI, tricyclic antidepressant, other), antipsychotic, or for medical problems. Medication-use frequencies in each category will be calculated and distributions inspected to decide if variables should be treated as binary (ie, presence/absence) or continuous (ie, number of each medication). As in our prior trials, change in each class of medications from baseline to 6 months will be quantified as (a) adding a new medication, (b) increasing the dosage/frequency of a medication, (c) discontinuing a medication, or (d) decreasing the dosage/frequency of use. Changes in medication use will be examined as potential mediators of the relationship between treatment group and 6-month outcomes to address person-centered questions related to the combined use of medication and CL/ECC.

Statistical analyses will occur at IQEST.

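### The 80% power claimed for a moderator R-square change of .03 does not follow from the medium-effect premise with 128 to 150 participants; it needs an unstated full-model R² of about .43 to .52

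*Combined protocol and SAP*

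**What the plan says.** G1, Exploratory Aims, is a single sentence. Its premise is "Assuming a medium effect size for models that include treatment group and an individual moderator", and its claim is that tests of treatment-by-moderator interaction on 6-month outcomes "will have 80% power to capture a change in R-square as small as .03". The sentence gives no N, no R² or f², and no list of covariates.

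The rest of G1 supplies the other design figures. On the error rate: "A 2-tailed type 1 error rate of 0.05 was used to calculate sample size". There are 64 per group (128 in total) for the main comparison, and 150 are randomised to allow for 15% attrition. Multiple imputation is meant to bring all randomised participants into the analysis.

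G2 describes a fuller model than the G1 sentence does. Under Heterogeneity of Treatment Effects, each moderator is tested by adding it and "the interaction term between treatment condition and the moderator in the ANCOVA models described previously". Those models are defined under Specific Aim 1: "All models will include treatment group (ie, CL versus ECC) as a predictor and respective baseline scores", together with variables that differ between groups at baseline. The heterogeneity section also cautions: "Although sample size may not be adequate to confirm sources of HTE, these exploratory analyses will allow us to describe patterns".

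**The concern.** An R-square change of .03 is a small effect for a trial of this size, and a main-effect design sized for d = .50 would not usually have 80% power for an interaction that small. The stated premise is a medium effect for a model with only treatment and one moderator. Such a model leaves most of the outcome variance unexplained, so it does little to sharpen the interaction test.

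What is at stake is how null interactions are read. G2 lists several candidate moderators: demographics, baseline symptoms, diagnoses and medication use. A reader who relies on the G1 sentence could take a non-significant interaction as good evidence against an effect of .03. On the stated premise, an effect of that size would be missed about 37–45% of the time. The reader also cannot tell which N and which R² the 80% rests on.

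**Working it through.** **Inputs from the documents (G1).** Two-sided alpha .05; N = 128 analysable or 150 randomised; change in R² (ΔR²) = .03; claimed power 80%.

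**Assumptions, not in the documents.**
- *Medium* is the conventional model R² of about .13, which becomes .16 once the .03 is added.
- The interaction has 1 degree of freedom.
- The baseline–outcome correlation r is varied from .3 to .65.

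**Check of the main calculation.** A two-sample t-test with 64 per group, d = .50 and two-sided .05 has power 80.1%. The plan's primary figure reproduces.

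**Formula for the interaction.** F test with 1 and N − k − 1 degrees of freedom, where k is the number of predictors, and noncentrality λ = N × ΔR² / (1 − R²_full).

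**(a) The model as the G1 sentence describes it** (treatment, moderator, interaction; k = 3).

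| N | R²_full | λ | Power for .03 |
|---|---|---|---|
| 128 | .13 | 128 × .03 / .87 = 4.41 | .550 |
| 128 | .16 | 128 × .03 / .84 = 4.57 | .564 |
| 150 | .13 | 150 × .03 / .87 = 5.17 | .618 |
| 150 | .16 | 150 × .03 / .84 = 5.36 | .633 |

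Solving for the ΔR² that has 80% power:
- N = 128: .051 if R² is .13 before the interaction, .054 if the total is .13.
- N = 150: .044 and .046 on the same two readings.

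These are about 1.5 to 1.8 times the stated .03 (.044/.03 = 1.47; .054/.03 = 1.8). Detecting .03 with 80% power would need N = 230 at R²_full = .13, or 222 at .16.

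**Other readings of the premise** (N = 128 / N = 150):
- *Medium* taken as d = .50 for treatment: R² = d²/(d² + 4) = .25/4.25 = .0588. Adding .03 gives R²_full = .089 and power .531 / .598.
- A conventionally large model (.26 + .03 = .29): .636 / .706.
- Alpha .10 with R²_full = .16: .685 / .745.
- N = 300 with R²_full = .16: .904. The 300 are people enrolled for screening, not an analysis set.

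None of these gives 80%. Changing k from 3 to 10 moves power by less than .002.

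**(b) The planned ANCOVA with the baseline score** (k = 4). Power of 80% needs λ of about 7.97 at N = 128 and 7.95 at N = 150. Then R²_full = 1 − N × .03 / λ:
- N = 128: 1 − 3.84/7.97 = .518.
- N = 150: 1 − 4.50/7.95 = .434.

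To see what baseline correlation that implies, take R²_full = r² + .0588 (treatment) + 0 to .03 (moderator main effect) + .03 (interaction):

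| r | Power, N = 128 | Power, N = 150 |
|---|---|---|
| .30 | .574–.589 | .643–.659 |
| .40 | .612–.629 | .681–.699 |
| .50 | .667–.687 | .736–.756 |
| .60 | .745–.768 | .810–.831 |
| .65 | .794–.819 | .854–.875 |

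Under this build-up, 80% requires r of about .63–.66 at N = 128 or .56–.59 at N = 150.

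**The case against.** The best defence is that the G1 sentence names the terms of interest, not every covariate. The test that will be run is the ANCOVA with the baseline score of the same outcome, plus any variables that differ between groups at baseline. On that reading 80% is attainable: at r = .6 and N = 150 the table shows 81–83%. The scenarios may also lean low, because they cap the moderator's main effect at .03 and give nothing to the other covariates. For illustration, with r = .5 and .09 for the moderator and other covariates together, R²_full is .25 + .0588 + .09 + .03 = .43, and power is about .80 at N = 150, though still .73 at N = 128.

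This stands as far as it goes: the shortfall in the planned model depends on inputs nobody has stated, and 55–63% is the low end. It does not rescue the sentence. The R² or correlation it would need appears nowhere in the documents and is not the premise the sentence gives. N = 150 is also the favourable end, since it counts imputed outcomes as if fully observed.

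It is also fair to say that G2's caution is not a direct contradiction. Power to detect one interaction of a given size is not the same as confirming sources of heterogeneity across several moderators. The caution is better read as a qualification that the G1 sentence lacks. Finally, these are exploratory analyses and no decision rule depends on them, which limits the weight of the point but does not make the figure correct.

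**Conclusion.** The concern holds. The stated 80% is about 17 to 25 percentage points above what the G1 premise delivers (80 − 63.3 = 16.7; 80 − 55.0 = 25.0). This rests on the conventional value for medium, which the documents do not give, but the conclusion does not hinge on it: a conventionally large model R² still falls short at both sample sizes. The claim can be true for the planned ANCOVA only if the full model explains about 52% (N = 128) or 43% (N = 150) of outcome variance. That may be reachable for some outcomes, but it is undisclosed.

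The consequence is confined to the exploratory moderator analyses. The primary sample size is unaffected.

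**What to change.** Restate the Exploratory Aims sentence in G1 in one of two ways.

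1. If the medium-effect premise is kept, state the R² it stands for. With R² of about .13, say that 80% power applies to an R-square change of about .05 (N = 128) or .045 (N = 150), and that power for .03 is about 55–63%.
2. If a larger R² from the baseline score was intended, state that R², its source, the covariates and the N, and give the matching power. Keeping .03 at 80% requires a full-model R² of about .52 at N = 128 or .43 at N = 150.

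The second is preferable if the planners can recover their inputs, because it describes the model that will be fitted. Under either option, add the caution from the heterogeneity section of G2 so that the two places say the same thing.

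The cost is one corrected statement. No more participants are needed, and the primary and secondary analyses do not change. Either the exploratory power becomes less favourable or the assumption behind it becomes visible.

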## G2. Data Analysis

Provide a description of your plan for data analysis. State the types of comparisons you plan (e.g. comparison of means, comparison of proportions, regressions, analysis of variance). Which is the PRIMARY comparison/analysis? How will the analyses proposed relate to the primary purposes of your study?

Analytic procedures were guided by PCORI Methodology Standards and best practices for clinical-trials research. Attempts will be made to minimize missing data with telephone-based assessments and person-centered treatment procedures that limit study attrition. We will use the SPSS 17.0 Missing Values Analysis function to determine type of missing data. If Little's MCAR test is not significant, missing data will be viewed as missing completely at random. If Little's MCAR test is significant, separate variance t-tests will be used to determine whether missing data are missing at random or missing not at random (MNAR). If the missingness mechanism is MNAR, the *dmiss* (ie, the standardized respondent-nonrespondent mean difference for a variable) and *f2miss* (ie, the standardized respondent-nonrespondent difference in the relationship between 2 variables) systematic nonresponse parameters will be estimated to determine the extent to which (and the direction in which) a parameter estimate is biased by the response rate. Low response rates will more greatly compromise external validity when *dmiss* and *f2miss* are large. Results may be interpreted cautiously in the context of the magnitude and nature of bias present. Additionally, missing data will be addressed using multiple imputation procedures PROC MI and MINANALYZE in SAS Version 9.3.167. Prior to analyses to address specific aims, the distributional nature of all variables will be assessed, and nonparametric tests (eg, Fisher's Exact Test; Mann-Whitney test), data transformations (eg, log linear), or other alternate methods (eg, weighted least-squares regressions, dichotomizing variables) will be conducted where appropriate. We will initiate data analyses by comparing baseline demographic and clinical variables (including medication use) between CL and ECC with chi-square and independent samples t-tests. Variables with *p* values < 0.25 will be included as control variables or propensity scores in subsequent models. We will then compare baseline demographic and clinical variables between study completers and noncompleters, using chi-square and independent samples t-tests.

Specific Aim 1. Examine the comparative effectiveness of CL and ECC in older adults with clinically significant worry on primary outcomes (worry, GAD-related symptoms). Primary outcome analyses at 6 months will be intention-to-treat (ITT) and will use the multiple imputation procedures PROC MI and MINANALYZE in SAS Version 9.3 to estimate missing observations. Another set of analyses will be for completers and will include only observed data. We will first employ Analysis of Covariance (ANCOVA) to examine treatment differences in worry and anxiety at 6 months (post intervention). We will conduct separate models for worry and anxiety. All models will include treatment group (ie, CL versus ECC) as a predictor and respective baseline scores and any demographic or clinical variables that differed between treatment groups at baseline as covariates. Treatment effect sizes will be calculated. We will calculate intraclass correlation coefficients (ICC) for both primary outcomes to determine the degree of clustering within referral source (social service or faith-based setting). If a substantial proportion of variability in either outcome is accounted for by referral source (ie, ICC greater than 0.10), multilevel models will be employed using SAS PROC MIXED to minimize the bias of error terms that may occur from dependency due to nesting effects. These models will include the intercept as a random effect and treatment group, respective baseline scores, and variables that differed between treatment groups at baseline as fixed effects.

Specific Aim 2. Examine the comparative effectiveness of CL and ECC on secondary outcomes (anxiety, depression, sleep, functional status, quality of life, service use). Analyses will be conducted as in Aim 1, first using ITT and multiple imputation to estimate missing data. Another set of analyses will be conducted for study completers. We will use ANCOVA to examine treatment differences at 6 months in secondary outcomes (anxiety, depression, sleep, functional status, quality of life, service use), using separate models for each measure. Effect sizes will be calculated. As in Aim 1, these models will include the intercept as a random effect and treatment group, baseline scores, and variables that differed between treatment groups at baseline

as fixed effects.

**Specific Aim 3.** Examine the maintenance of outcomes in CL and ECC. Analyses for all primary and secondary outcomes will be repeated to examine treatment differences in outcomes at 9 months. All procedures will be as previously described.

**Analysis of Implementation Potential.** Differences in satisfaction between CL and ECC at 6 and 9 months will be examined with either an independent samples t-test or ANCOVA (if covariates are warranted). Descriptive data that address reach, participant initiation and engagement, and treatment fidelity will be reviewed by the CLC. CLC input will be used to modify the model of care if needed and to develop implementation strategies. Participant representativeness (vs. excluded participants and partner caseloads) will be examined with chi-square tests (ordinal variables) and independent sample t-tests (interval variables).

Qualitative data will be analyzed with framework analysis, whereby themes generating from both a priori issues and data are identified. Digital recordings of each qualitative interview will be transcribed verbatim into text. Transcripts will be imported into Atlas.ti to facilitate storing, management, and visualization. First, we will check transcripts for accuracy. Then, all data will be analyzed, and contact summary sheets completed after each interview, to establish a thematic framework. Raters will compare coding across transcripts and discuss/reconcile dissimilar coding. From the categories, themes within and across groups will be identified. Data analysis will identify recurring and important themes regarding acceptability, facilitators, and barriers. Descriptive statistics will characterize demographic data.

**Heterogeneity of Treatment Effects (HTE).** According to PCORI Methodology Standards, exploratory analyses will examine HTE to address for whom and under what conditions CL may be optimally useful. Although sample size may not be adequate to confirm sources of HTE, these exploratory analyses will allow us to describe patterns that can be examined in subsequent larger studies. HTE variables of interest include potential moderators and mediators of treatment effects. Potential moderators include demographics, baseline symptoms (PSWQ, PHQ-8), presence-absence of DSM diagnoses (anxiety disorders, depression), and baseline medication use. Moderation will be tested by including each separate moderator and the interaction term between treatment condition and the moderator in the ANCOVA models described previously. A significant interaction between treatment group and moderator will indicate that differences in treatment effects depend on the moderator. Simple slopes analyses will be conducted to follow-up significant interactions. Potential mediators include change in self-reported use of medication. Medications will be characterized as in our prior trials as antianxiety (benzodiazepine, buspirone, or other), antidepressant (SSRI, SNRI, tricyclic antidepressant, other), antipsychotic, or for medical problems. Medication-use frequencies in each category will be calculated and distributions inspected to decide if variables should be treated as binary (ie, presence/absence) or continuous (ie, number of each medication). As in our prior trials, change in each class of medications from baseline to 6 months will be quantified as (a) adding a new medication, (b) increasing the dosage/frequency of a medication, (c) discontinuing a medication, or (d) decreasing the dosage/frequency of use. Changes in medication use will be examined as potential mediators of the relationship between treatment group and 6-month outcomes to address person-centered questions related to the combined use of medication and CL/ECC.

Statistical analyses will occur at IQEST.

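### Tests on observed data cannot label missingness MCAR, MAR or MNAR, and no planned analysis re-estimates the 6-month effect under MNAR

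*Combined protocol and SAP*

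**What the plan says.** Section G2 gives a sequence for missing data. If Little's "test is not significant, missing data will be viewed as missing completely at random". If it is significant, "separate variance t-tests will be used to determine whether missing data are missing at random or missing not at random (MNAR". If the label is MNAR, two nonresponse parameters are estimated: dmiss, defined as "the standardized respondent-nonrespondent mean difference for a variable", and f2miss, its counterpart for the relationship between two variables. The stated consequence is "Results may be interpreted cautiously in the context of the magnitude and nature of bias present".

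Apart from that sequence, "missing data will be addressed using multiple imputation procedures PROC MI and MINANALYZE in SAS", and Specific Aim 1 makes imputation the 6-month intention-to-treat analysis. Three other checks appear:

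- G2, Specific Aim 1: "Another set of analyses will be for completers and will include only observed data".
- G2: "We will then compare baseline demographic and clinical variables between study completers and noncompleters".
- G1 (Sample Size): "If differential study attrition occurs across groups, measures different by attrition status will be included as covariates in effectiveness outcome analyses".

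G1 also says that reasons for withdrawal will be recorded. Specific Aim 3 repeats the procedures at 9 months.

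**The concern.** There are two separate gaps.

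**The labelling rule.** Under MAR, missingness may depend on observed values. Under MNAR it also depends on the unseen value, here the 6-month score. A t-test of an observed variable between people with and without that score never touches the unseen value. A difference is evidence against MCAR, and both MAR and MNAR can produce it. The plan also does not say which t-test result leads to which label. A non-significant Little's test is only a failure to reject MCAR.

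The MNAR branch does not repair this. For a missing 6-month outcome, dmiss and f2miss need nonrespondents' 6-month values, which do not exist. They can be computed for baseline variables, but that says nothing direct about the outcome. The branch produces no re-estimated treatment effect.

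**No MNAR analysis of the primary result.** Imputation as described, attrition covariates and the completers analysis all rest on MAR or something stronger. If they agree, that does not bear on MNAR.

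At stake are an unsupported sentence about mechanism attached to the primary result, and a reader unable to judge how far that result depends on MAR.

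**Working it through.** **Inputs from G1.** Two-sided alpha 0.05; 64 per group for 80% power at d = .50; 75 per group randomised; attrition 15% expected, 12% in the pilot, 19% to 25% in earlier studies; prior primary effects .40 to .50.

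**The plan's own figure.** The two-sample t-test formula gives 63.8, so 64 per group (power .801). 64 / 0.85 = 75.3, against 75 stated. The sample size reproduces. Missing 6-month scores out of 150: 18 at 12%, 22.5 at 15%, 28.5 at 19%, 37.5 at 25%.

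**Step 1: what the labelling sequence does.** 3,000 simulated trials per setting, n = 150, about 15% of 6-month scores missing. Assumed, because the documents give no values: correlation .6 between the 6-month score and its baseline, pairwise correlation .4 among baseline variables, logistic missingness with slope 1 or 0.5 per SD. Little's test is followed by Welch t-tests on 1, 5 or 12 baseline variables.

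| True mechanism | Labelled MCAR, slope 1 (1 / 5 / 12 variables) | Slope 0.5 |
|---|---|---|
| MAR on baseline | 3% / 13% / 30% | 45% / 70% / 82% |
| MNAR on the 6-month score | 33% / 63% / 78% | 77% / 87% / 92% |
| MNAR on the part unrelated to baseline | about 95% in each case | not tabulated |

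Repeat runs at slope 1 moved these by at most 4 percentage points. The MNAR-on-score row depends on the assumed correlation: with one baseline variable at slope 1 and 15% missing, the MCAR label was given in 80%, 51% and 21% of trials at r = .3, .5 and .7.

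When Little's test was significant (slope 1), at least one t-test was also significant in 99% to 100% of MAR trials and 93% to 98% of MNAR-on-score trials. The second step therefore does not separate the two.

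**Step 2: when MNAR dropout biases the comparison.** Baseline-adjusted analysis of observed data, slope 1, r from .3 to .7:

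- Dropout driven by the residual in CL only: bias toward CL of 0.11 to 0.15 SD at 15% missing and 0.17 to 0.22 SD at 25%. The label was still MCAR in 94% to 95% of trials.
- The same residual mechanism in both arms: bias about zero.
- Dropout driven by the 6-month score in both arms: bias of 0.02 to 0.06 SD against CL.

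**Step 3: how far the conclusion could move.** Let m be the missing fraction and delta the number of SDs by which CL dropouts are worse than imputed, with ECC dropouts as imputed.

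- Shifted effect = d − m × delta. At delta = 0.5: .50 − .15 × 0.5 = .425; .50 − .25 × 0.5 = .375.
- Tipping delta = (d − t × SE) / m, where SE = √(2/n) × √(1 − r²) and n = 75(1 − m).
- Example: m = .15, n = 63.75, r = 0, SE = .177, t = 1.979, so t × SE = .351 and delta = (.50 − .351)/.15 = 1.0 SD.

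| Missing | d = .50, r = 0 | d = .50, r = .6 | d = .40, r = 0 | d = .40, r = .6 |
|---|---|---|---|---|
| 12% | 1.30 | 1.87 | 0.46 | 1.04 |
| 15% | 1.00 | 1.46 | 0.33 | 0.80 |
| 19% | 0.74 | 1.12 | 0.21 | 0.59 |
| 25% | 0.51 | 0.80 | 0.11 | 0.40 |

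Taking n = 75 in the SE raises each value by about 0.14 to 0.20 SD. As a check on the formula, multiple imputation with Rubin's rules (150 trials, 30 imputations, r = .6) gave mean SEs of .142 and .151 at 15% and 25% missing, matching the formula. At delta = 0.5 the estimate fell by about .075 and .12.

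**The case against.** The strongest reply has four parts.

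- **The label changes no number.** Imputation runs regardless, so the estimate, confidence interval and p-value are untouched. This stands: the first gap concerns what the report may claim about mechanism, not the estimate.
- **The tipping figures shift CL only.** A false benefit for CL needs MNAR dropout that differs by arm, and the same mechanism in both arms gave little bias or bias against CL (step 2). Both arms also have the same telephone assessments. This stands as a limit on how likely harm is. It does not remove the gap. The arms differ in contact (up to 12 CL sessions in the first 3 months against brief ECC check-in calls), and G1 itself provides for differential attrition, though only through observed covariates.
- **The simulations rest on assumed correlations and slopes.** This is true, and the mislabelling rates move a good deal with them. The logical point needs no simulation.
- **MNAR was considered.** Reasons for withdrawal are recorded, dmiss and f2miss aim at the size and direction of bias, and 9-month scores could inform Little's test for those who miss only the 6-month visit. These help description. None supplies the unseen 6-month values or re-estimates the effect under a stated departure from MAR.

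**Conclusion.** The concern holds. The classification rule is wrong as written: neither Little's test nor the t-tests can do what the plan asks of them, and dmiss and f2miss are not identified for unseen 6-month outcomes. The missing MNAR sensitivity analysis is a separate gap that is cheap to close. Neither point invalidates the primary analysis, which remains a reasonable one under MAR.

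In size, the CL-only tipping shift runs from comfortable (1.87 SD at 12% missing, d = .50, r = .6) to very small (0.11 SD at 25% missing, d = .40, no baseline adjustment). At the planned 15% and d = .50 it is 1.0 to 1.5 SD. These figures assume a shift in one arm, an SE held fixed, and r of 0 or .6. The trial's own value could lie anywhere in the range, and no planned output would show where. This should be fixed before the data are analysed.

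**What to change.** 1. Delete the test-based MCAR/MAR/MNAR labelling and the dmiss/f2miss branch that depends on it. Little's test, the completer versus noncompleter comparison and the reasons for withdrawal may stay as description.
2. State MAR, given the variables in the imputation model, as the assumption behind PROC MI.
3. Prespecify, whatever any test shows, a delta-adjusted tipping-point analysis for both primary outcomes at 6 months. Shift imputed scores toward worse by 0 to 2 SD in steps of 0.25 SD, in CL only, ECC only and both arms; recombine with PROC MIANALYZE; and report the delta at which the conclusion changes beside the MAR and completers results. The grid is a convention and can be altered.
4. Define the SD in advance. The pooled observed 6-month SD is sensible, because entry requires a PSWQ score of 50 or more and this narrows the baseline spread. State beforehand what shift would be considered plausible.

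The cost is a few lines of SAP text, a short data step after the planned imputation and one extra table per primary outcome. No participants or data are added. The same step could be reused at 9 months for Specific Aim 3.
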